5.1.1.2 Dose Modifications and Dosing Delays Tables for Specific Adverse Events for Pembrolizumab

Subjects should receive appropriate supportive care measures as deemed necessary by the treating investigator including but not limited to the items outlined below:

- **Diarrhea:** Subjects should be carefully monitored for signs and symptoms of enterocolitis (such as diarrhea, abdominal pain, blood or mucus in stool, with or without fever) and of bowel perforation (such as peritoneal signs and ileus). In symptomatic subjects, infectious etiologies should be ruled out, and if symptoms are persistent and/or severe, endoscopic evaluation should be considered.
 - In subjects with severe enterocolitis (Grade 3), pembrolizumab will be permanently discontinued and treatment with systemic corticosteroids should be initiated at a dose of 1 to 2 mg/kg/day of prednisone or equivalent. When symptoms improve to Grade 1 or less, corticosteroid taper should be started and continued over at least 1 month.
 - In subjects with moderate enterocolitis (Grade 2), pembrolizumab should be withheld and anti-diarrheal treatment should be started. If symptoms are persistent for more than one week, systemic corticosteroids should be initiated (e.g., 0.5 mg/kg/day of prednisone or equivalent). When symptoms improve to Grade 1 or less, corticosteroid taper should be started and continued over at least 1 month. Regarding guidelines for continuing treatment with pembrolizumab, see Section 5.2.
 - All subjects who experience diarrhea should be advised to drink liberal quantities of clear fluids. If sufficient oral fluid intake is not feasible, fluid and electrolytes should be substituted via IV infusion.
- **Nausea/vomiting:** Nausea and vomiting should be treated aggressively, and consideration should be given in subsequent cycles to the administration of prophylactic antiemetic therapy according to standard institutional practice. Subjects should be strongly encouraged to maintain liberal oral fluid intake.
- **Anti-infectives:** Subjects with a documented infectious complication should receive oral or IV antibiotics or other anti-infective agents as considered appropriate by the treating investigator for a given infectious condition, according to standard institutional practice.
- **Immune-related adverse events:** Please see Section 5.2.2 below and the separate guidance document in the administrative binder regarding diagnosis and management of adverse experiences of a potential immunologic etiology. Specific immune-related adverse events (irAEs) will be collected and designated as immune-related events of clinical interest (ECIs) as described in Section 5.2.2.
- **Management of Infusion Reactions:** Acute infusion reactions (which can include cytokine release syndrome, angioedema, or anaphylaxis) are different from allergic/hypersensitive reactions, although some of the manifestations are common to both AEs. Signs and symptoms usually develop during or shortly after drug infusion and generally resolve completely within 24 hours of completion of infusion. Signs/symptoms may include: Allergic reaction/hypersensitivity (including drug fever); Arthralgia (joint pain); Bronchospasm; Cough; Dizziness; Dyspnea (shortness of breath); Fatigue (asthenia, lethargy, malaise); Headache; Hypertension; Hypotension; Myalgia (muscle pain); Nausea; Pruritis/itching; Rash/desquamation; Rigors/chills; Sweating (diaphoresis); Tachycardia; Tumor pain (onset or exacerbation of tumor pain due to treatment); Urticaria (hives, welts, wheals); Vomiting.

Table 5.1 below shows treatment guidelines for subjects who experience an infusion reaction associated with administration of pembrolizumab.

Table 5.1 Infusion Reaction Treatment Guidelines

NCI CTCAE Grade	Treatment	Premedication at subsequent dosing

Grade 1 Mild reaction; infusion interruption not indicated; intervention not indicated
	
Increase monitoring of vital signs as medically indicated until the subject is deemed medically stable in the opinion of the investigator.
	
None


Grade 2 Requires infusion interruption but responds promptly to symptomatic treatment (e.g., antihistamines, NSAIDs, narcotics, IV fluids); prophylactic medications indicated for < =24 hrs
	
Stop Infusion and monitor symptoms. Additional appropriate medical therapy may include but is not limited to: IV fluids Antihistamines NSAIDs Acetaminophen Narcotics
 
Increase monitoring of vital signs as medically indicated until the subject is deemed medically stable in the opinion of the investigator.
 
If symptoms resolve within one hour of stopping drug infusion, the infusion may be restarted at 50% of the original infusion rate (e.g. from 100 mL/hr to 50 mL/hr). Otherwise dosing will be held until symptoms resolve and the subject should be premedicated for the next scheduled dose.
 
Subjects who develop Grade 2 toxicity despite adequate premedication should be permanently discontinued from further trial treatment administration.
	
Subject may be premedicated 1.5h (± 30 minutes) prior to infusion of pembrolizumab with:
 
Diphenhydramine 50 mg po (or equivalent dose of antihistamine).
 
Acetaminophen 500-1000 mg po (or equivalent dose of antipyretic).

Grades 3 or 4 Grade 3: Prolonged (i.e., not rapidly responsive to symptomatic medication and/or brief interruption of infusion); recurrence of symptoms following initial
	
Stop Infusion. Additional appropriate medical therapy may include but is not limited to: IV fluids Antihistamines NSAIDs
	
No subsequent dosing

NCI CTCAE Grade	Treatment	Premedication at subsequent dosing
improvement; hospitalization indicated for other clinical sequelae (e.g., renal impairment, pulmonary infiltrates) Grade 4: Life-threatening; pressor or ventilatory support indicated	Acetaminophen Narcotics Oxygen Pressors Corticosteroids Epinephrine Increase monitoring of vital signs as medically indicated until the subject is deemed medically stable in the opinion of the investigator. Hospitalization may be indicated. Subject is permanently discontinued from further trial treatment administration.	
Appropriate resuscitation equipment should be available in the room and a physician readily available during the period of drug administration. For Further information, please refer to the Common Terminology Criteria for Adverse Events v4.0 (CTCAE) at http://ctep.cancer.gov		

5.1.1.3 Supportive Care Guidelines for Pneumonitis

Subjects with symptomatic pneumonitis should immediately stop receiving pembrolizumab and have an evaluation. The evaluation may include bronchoscopy and pulmonary function tests to rule out other causes such as infection. If the subject is determined to have study drug associated pneumonitis, the suggested treatment plan is detailed in Table 5.12.

Table 5.12 Recommended Approach to Handling Pneumonitis

Study drug associated pneumonitis	Withhold/Discontinue pembrolizumab?	Supportive Care
Grade 1 (asymptomatic)	No action	Intervention not indicated
Grade 2	Withhold pembrolizumab, may return to treatment if improves to Grade 1 or resolves within 12 weeks	Systemic corticosteroids are indicated. Taper if necessary.
Grade 3 and Grade 4	Discontinue pembrolizumab	Systemic corticosteroids are indicated. The use of infliximab may be indicated as appropriate. Refer to the Event of Clinical Interest and Immune-related Adverse Event Guidance Document for additional recommendations.

For Grade 2 pneumonitis that improves to \leq Grade 1 within 12 weeks, the following rules should apply:

- First episode of pneumonitis
 - May increase dosing interval by one week in subsequent cycles
- Second episode of pneumonitis – permanently discontinue pembrolizumab if upon rechallenge subject develops pneumonitis \geq Grade 2

5.2 Monitoring and Toxicity Management

Each patient receiving pembrolizumab in combination with Tamoxifen and Vorinostat will be evaluable for safety. The safety parameters include all laboratory tests and hematological abnormalities, physical findings, and spontaneous reports of adverse events reported to the investigator by patients.

Each patient will be assessed periodically for the development of any toxicity as outlined in [Section 6 Study Procedures and Observations](#). Toxicity will be assessed according to the NCI [CTCAE v4.0](#). Dose adjustments will be made according to the system showing the greatest degree of toxicity.

5.2.2 Events of Clinical Interest

Selected non-serious and serious adverse events are also known as Events of Clinical Interest (ECI) and must be reported to the Sponsor.

For the time period beginning when the consent form is signed until treatment allocation/randomization, any ECI, or follow up to an ECI, that occurs to any subject must be reported within 24 hours to the Sponsor if it causes the subject to be excluded from the trial, or is the result of a protocol-specified intervention, including but not limited to washout or discontinuation of usual therapy, diet, placebo treatment or a procedure.

For the time period beginning at treatment allocation/randomization through 30 days following cessation of treatment if the subject initiates new anticancer therapy, whichever is earlier, any ECI, or follow up to an ECI, whether or not related to the Sponsor's product, must be reported within 24 hours to the Sponsor, either by electronic media or paper. Electronic reporting procedures can be found in the EDC data entry guidelines. Paper reporting procedures can be found in the Investigator Trial File Binder (or equivalent).

Events of Clinical Interest for this trial include:

1. an overdose of Sponsor's product, as defined in Section 7.8.1 - Definition of an Overdose for This Protocol and Reporting of Overdose to the Sponsor, that is not associated with clinical symptoms or abnormal laboratory results.
2. an elevated AST or ALT lab value that is greater than or equal to 3X the upper limit of normal and an elevated total bilirubin lab value that is greater than or equal to 2X the upper limit of normal and, at the same time, an alkaline phosphatase lab value that is less than 2X the upper limit of normal, as determined by way of protocol-specified laboratory testing or unscheduled laboratory testing.*

*Note: These criteria are based upon available regulatory guidance documents. The purpose of the criteria is to specify a threshold of abnormal hepatic tests that may require an additional evaluation for an underlying etiology. The trial site guidance for assessment and follow up of these criteria can be found in the Investigator Trial File Binder (or equivalent).

6 Study Procedures and Observations

6.1 Treatment Duration

Eligible patients will receive treatment as described above, in consecutive 3-week cycles, until progression of disease or unacceptable toxicity. Patients are expected to receive treatment for at least 3 cycles, at which time the first evaluation for efficacy will occur. If there is continued safety and tolerability, treatment may continue.

For Arm A: After the initial treatment with vorinostat and tamoxifen, regardless of response of the staging studies, PD-1 will be added to all patients.

For Arm B: patients may remain on study if there is radiological progression however the clinical presentation shows improvement or benefit.

All patients will be restaged during week 9 and 18 via imaging scans, staging will then be continued every 3 cycles until 6 months. After 6 months staging may be spaced out to 6 cycles if clinically indicated.

Patients will be followed for evaluation of safety for at least 30 days after the last dose of study drug. Any study drug-related serious adverse events will be followed until resolution, return to baseline grade, or deemed irreversible by the Investigator.

Subjects who experience a recurrence of the same severe or life-threatening event at the same grade or greater with re-challenge of pembrolizumab should be discontinued from trial treatment.

6.2 Schedule of Procedures and Observations

The study-specific assessments are detailed in this section and outlined in [Section 6 Schedule of Study Procedures and Assessments](#). Screening assessments must be performed within 28 days prior to the first dose of investigational product. Any results falling outside of the reference ranges may be repeated at the discretion of the investigator. All on-study visit procedures are allowed a window of ± 5 days unless otherwise noted. Treatment or visit delays for public holidays or weather conditions, or patient's personal reasons that do not compromise safety do not constitute a protocol violation. Treatment delays may not exceed 3 weeks, unless discussed with the study team for patients with documented benefit. Patients with proven systemic benefit, who have localized progression in the sanctuary site, may receive localized treatment to that site, including but not limited to radiation therapy, gamma knife or surgery.

A written, signed, informed consent form (ICF) and a Health Insurance Portability and Accountability Act (HIPAA) authorization must be obtained before any study-specific assessments are initiated. A copy of the signed ICF will be given to the subject and a copy will be filed in the medical record. The original will be kept on file with the study records.

All patients who are consented will be registered in OnCore®, the UCSF Helen Diller Family Comprehensive Cancer Center Clinical Trial Management System (CTMS). The system is password protected and meets HIPAA requirements.

6.2.2 Long Term/Survival Follow-up Procedures

Safety Follow-Up Visit

The mandatory Safety Follow-Up Visit should be conducted approximately 30 days after the last dose of trial treatment or before the initiation of a new anti-cancer treatment, whichever comes first. All AEs that occur prior to the Safety Follow-Up Visit should be recorded. Subjects with an

AE of Grade > 1 deemed related to study drug, will be followed until the resolution of the AE to Grade 0-1, baseline or until the beginning of a new anti-neoplastic therapy.

Follow-up Visits

Subjects who discontinue trial treatment for a reason other than disease progression will move into the follow-up phase and should be assessed every 12 weeks (\pm 7 days) by radiologic imaging to monitor disease status. Every effort should be made to collect information regarding disease status until the start of new anti-neoplastic therapy, disease progression, death, end of the study or if the subject begins retreatment with pembrolizumab. Information regarding post-study anti-neoplastic treatment will be collected if new treatment is initiated.

Survival Follow-up

Once a subject experiences confirmed disease progression or starts a new anti-cancer therapy, the subject moves into the survival follow-up phase and should be contacted by telephone every 12 weeks to assess for survival status until death, withdrawal of consent, or the end of the study, whichever occurs first.

6.2.3 Discontinuation of Therapy

The Investigator will withdraw a patient whenever continued participation is no longer in the patient's best interests. Reasons for withdrawing a patient include, but are not limited to, disease progression, the occurrence of an adverse event or a concurrent illness, a patient's request to end participation, or simply significant uncertainty on the part of the Investigator that continued participation is prudent. There may also be administrative reasons to terminate participation, such as concern about a patient's compliance with the prescribed treatment regimen.

When a subject discontinues/withdraws prior to trial completion, all applicable activities scheduled for the final trial visit should be performed at the time of discontinuation. Any adverse events which are present at the time of discontinuation/withdrawal should be followed in accordance with the safety requirements outlined in Section 7.2 - Assessing and Recording Adverse Events. Subjects who a) attain a CR or b) complete 24 months of treatment with combination of vorinostat, tamoxifen or pembrolizumab may discontinue treatment with the option of restarting treatment if they may derive further benefit in the opinion of the study team. Tamoxifen should be continued. After discontinuing treatment following assessment of CR, these subjects should return to the site for a Follow-up Visit every 12 weeks with staging studies as described for patients on active treatment.

Table 6. Study Calendar

Test/Study	Baseline ^a screening	Cycle 1				Cycle 2	Subsequent cycles ^g	Restaging or off study
		D1	D8	D10 -12	D15	D1		
History	X	X	X		X	X	X	
Concomitant medication	X	X	X		X	X	X	
Physical Exam, Vitals & ECOG	X	X	X		X	X	X	
Height and weight	X	X	X		X	X	X	
Toxicity Assessment	X	X	X		X	X	X	X ^b
PK sample	X or D1 ^f			X ^h			X ^f (end of cycle 3)	
Tumor FNA/Biopsy	X or D1 ^f						X ^f (end of cycle 3)	
PBMC	X or D1 ^f			X ^h			X ^f (end of cycle 3)	
Lymphocyte Subset	X or D1 ^f			X ^h			X ^f (end of cycle 3)	
CBC w/diff	X	X	X		X	X	X	
Comprehensive metabolic panel ⁱ	X	X	X		X	X	X ^c	
Thyroid Function	X					X	X(odd cycles)	
CEA, Ca15-3, Ca 125 (If clinically indicated)	X	X				X	X ^c	
Pregnancy Test	X ^d						X ^d	
Radiology (CT scans, MRI)	X ^e						X ^e	X ^e
Documentation of Response							X	
Vorinostat	400 mg once a day, 5 days on, 2 days off, weekly every cycle							
Tamoxifen	20 mg once a day continuously (for ER+ disease only)							
Pembrolizumab Arm A)	200 mg q every three weeks start on day 1 of cycle 1							
Pembrolizumab Arm B)	200 mg q every three weeks start on day 1 of cycle 2							

a) All screening procedures must be performed within 28 days unless otherwise indicated. Pre-study tests, History and Physical may be used for Day 1 tests if within 2 weeks

- b) Toxicity assessment must be performed until all treatment-related toxicities have been resolved or decreased to grade 1. Adverse events must be recorded up to 30 days after termination on study
- c) Every month for the first 6 cycles, then at least every 3 cycles thereafter, more frequently if clinically indicated
- d) For women of childbearing potential, performed within 7 days of starting treatment. Pregnancy test will be repeated if clinically indicated.
- e) Staging studies within 30 days prior to day of start, restaging after cycle 3 (week 9), 6 (week 18), then 9, 12, then every 6 cycles if clinically indicated. Partial and complete responses must be confirmed at least one month apart from the first documentation of objective response. Scans may be performed more frequently if clinically indicated.
- f) Pre-study within 14 days, and end of cycle 3 (preferably day 17-19) prior to cycle 4 day 1 pembrolizumab infusion.
- g) Cycle delays up to 5 days for non-medical reason (e.g. holidays) are acceptable without notification of regulatory agencies.
- h) On day 10-12 pre-dose.
- i) Sodium, Potassium, Chloride, blood urea nitrogen, Creatinine, Non-fasting glucose, Calcium, Magnesium, Phosphorus, ALT, AST, Alkaline Phosphatase, Albumin, Total Bilirubin, Total Protein
- j) Therapy delay for palliative radiation should be based on discussion with the study sponsor and the treating physician, every effort should be made not to hold therapy, patients where vorinostat is being held for more than 4 weeks may stay on study if there is felt to be a benefit

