Because vorinostat's dose limiting toxicities are anorexia, dehydration, diarrhea, and fatigue, patients should maintain adequate fluid and food intake. Encourage patients to seek a nutritional consult. Treat diarrhea promptly with appropriate supportive care, including loperamide. Instruct patients to begin taking loperamide at the first signs of: 1) poorly formed or loose stool, 2) occurrence of more bowel movements than usual in one day, or 3) unusually high volume of stool. Loperamide should be taken in the following manner: 4 mg at first onset of diarrhea, then 2 mg after each unformed stool. Daily dose should not exceed 16 mg/day. Loperamide should not be taken prophylactically. Advise patients to drink plenty of clear fluids to help prevent dehydration caused by diarrhea. Avoid loperamide if there is the presence of blood or mucus in the stool or if diarrhea is accompanied by fever. If grade 3 or 4 diarrhea develops, discontinue further treatment with vorinostat. Patients should not have taken valproic acid, another histone deacetylase inhibitor, for at least 2 weeks prior to study enrollment.

How Supplied:

Vorinostat is supplied by Merck & Co., Inc. Vorinostat will be provided in a 100-120 tablet bottle. For the purpose of this study, vorinostat will be given at 400 mg per day (4x 100 mg tablets), 5 of 7 days. Please refer to complete prescribing information in the FDA packet insert for storage and handling.

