5.1.1.1 Dose Modifications and Dosing Delays Tables for Drug Related Adverse Events

Hematologic toxicity

Neutropenia:

Neutropenia	Vorinostat	Tamoxifen
Febrile neutropenia		
ANC \geq 1000	100%	100%
ANC: 500-1000	Hold for until \leq grade 2 #, Restart at 75%: 300 mg qd for all subsequent cycles Second occurrence resume at 200 mg qd for all subsequent cycles Third occurrence: remove from study	100%
ANC: 0-500	Hold for until \leq grade 2 or less# Restart at 75%: 300 mg qd for all subsequent cycles Second occurrence resume at 200 mg qd for all subsequent cycles Third occurrence: remove from study	100%

#Patient with a dose delay for more than 3 weeks in the first 2 cycles will need to be replaced for toxicity and efficacy assessments.

Patients who developed a second episode of **febrile neutropenia** despite a dose modification will be removed from study.

Anemia

Hemoglobin	Vorinostat	Tamoxifen
>8 mg/dl	100 %: 400 mg qd	100%

6.5-8 mg/dl	75 %: 300 mg qd	100%
<6.5 mg/dl	50 %: 200 mg qd	100%

An alternative to dose modification would be the use of PRBC transfusion. This is not allowed in cycle one, but may be used at the discretion of the treating physician for subsequent cycles.

Thrombocytopenia

Platelets	Vorinostat	Tamoxifen
>75'000	100 %: 400 mg qd	100%
≤75'000	100 %: 400 mg qd	100%
≤50'000/mm ³	Hold until ≤grade 2 or less Restart at 75%: 300 mg qd for all subsequent cycles Second occurrence resume at 200 mg qd for all subsequent cycles Third occurrence: remove from study_	100%
≤25'000/mm ³	Hold until ≤grade 2 or less Restart at 75%: 300 mg qd for all subsequent cycles Second occurrence resume at 200 mg qd for all subsequent cycles Third occurrence: remove from study	100%

Non-hematological toxicities

Laboratory abnormalities must be clinically relevant and dose and drug related to prompt dose modifications.

Bilirubin	Vorinostat	Tamoxifen
≤1.5 mg/dl	100 %: 400 mg qd	100%
1.6 – 3.0 mg/dl	75 %: 300 mg qd	100%

>3.0 mg/dl	First occurrence: hold until \leq grade 2, 75 %: 300 mg qd Second occurrence: Hold until grade 2 or less, 50 %: 200 mg qd	100%
AST/ALT	Vorinostat	Tamoxifen
\leq 2.5 x ULN	100 %: 400 mg qd	100%
2.5-5 x ULN	First occurrence: 75 %: 300 mg qd Second occurrence: 50 %: 200 mg qd	100%

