> 5 x ULN	First occurrence: hold until \leq grade 2, resume at 75 %: 300 mg qd Second occurrence: Hold until grade 2 or less, 50 %: 200 mg qd Third occurrence: remove from study	100%

Hepatic Dysfunction: Any new increase in LFTs should raise the concern to rule out progressive metastatic disease. If the rise is not due to progressive metastatic disease, give the following dose based on lab values obtained on day 1 of each cycle:

Effects on the liver: Tamoxifen has been associated with changes in liver enzyme levels, and on rare occasions, a spectrum of more severe liver abnormalities including fatty liver, cholestasis, hepatitis and hepatic necrosis. A few of these serious cases included fatalities. In most reported cases, the relationship to tamoxifen was uncertain. However, some positive rechallenges and dechallenges have been reported. If grade 3 or 4 liver toxicity is maintained after a temporary stopping of vorinostat, both drugs should be stopped. Any rechallenge should be discussed with the study chair. **If treatment is delayed for more than 3 weeks, contact the Principle Investigator.**

Gastrointestinal Toxicity

Nausea/Vomiting/Dehydration: In this protocol, the routine use of any and all anti-emetics is allowed as clinically appropriate; these include the use of dexamethasone and 5-HT3 receptor antagonists.

Patients should maintain adequate fluid and food intake because vorinostat's dose-limiting toxicities are anorexia, dehydration, diarrhea, and fatigue. In the setting of dysgeusia, popsicles and Gatorade have been found to be useful by some investigators to maintain adequate hydration. Patients should also be encouraged to seek a nutritional consult.

Diarrhea: Treat diarrhea promptly with appropriate supportive care, including loperamide. Instruct patients to begin taking loperamide at the first signs of: 1) poorly formed or loose stool, 2) occurrence of more bowel movements than usual in one day, or 3) unusually high volume of stool. Loperamide should be taken in the following manner: 4 mg at first onset of diarrhea then 2 mg after each unformed stool. The daily dose should not exceed 16 mg. Loperamide should not be taken prophylactically. Advise patients to drink plenty of clear fluids to help prevent dehydration caused by diarrhea. Avoid loperamide if there is the presence of blood or mucus in the stool or if

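### After cycle 6 the calendar requires liver tests only every 63 days, so a first silent, clinically relevant, drug-related rise could be found up to 42 days later than with per-cycle testing

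*Combined protocol and SAP*

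**What the plan says.** Table 6 (Study Calendar, printed in 6.2.3) has a row for the "Comprehensive metabolic panel". Footnote i lists its contents, which include ALT, AST, alkaline phosphatase and total bilirubin. No other row measures them. In the column for subsequent cycles the row carries footnote c: "Every month for the first 6 cycles, then at least every 3 cycles thereafter, more frequently if clinically indicated". In the same column the CBC row is marked for every cycle and thyroid function for odd cycles.

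Section 5.1.1.1 gives vorinostat rules on these values. AST/ALT of 2.5-5 x ULN calls for a reduction to 300 mg at first occurrence, and above 5 x ULN for a hold. Bilirubin of 1.6-3.0 mg/dl calls for 300 mg, and above 3.0 mg/dl for a hold. The Hepatic Dysfunction paragraph says "Any new increase in LFTs should raise the concern to rule out progressive metastatic disease". It continues "If the rise is not due to progressive metastatic disease, give the following dose based on lab values obtained on day 1", and the sentence ends by referring to each cycle. A general limit also applies: "Laboratory abnormalities must be clinically relevant and dose and drug related to prompt dose modifications".

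Section 5.2.2, item 2, defines a hepatic event of clinical interest. It combines "an elevated AST or ALT lab value that is greater than or equal to 3X the upper limit of normal" with a bilirubin and an alkaline phosphatase criterion, "as determined by way of protocol-specified laboratory testing or unscheduled laboratory testing". It is reportable within 24 hours.

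**The concern.** The triggers in 5.1.1.1 are laboratory values, not symptoms, so the rule can start only if a sample is taken. After cycle 6 the required interval for that sample is three times the dosing cycle. The liver panel becomes the least frequent routine safety blood test: CBC every 21 days, thyroid function every 42, liver tests every 63.

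Most situations are covered. A known rise can be followed more often under footnote c, and a symptomatic patient should be picked up by the history, examination and toxicity assessment done every cycle. What remains is a first rise, without symptoms, arising between panels. Nothing in the calendar then prompts a test.

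Three things could be late: the vorinostat reduction or hold, recognition of the hepatic event of clinical interest and so its report, and the search for progression that a new rise is meant to prompt. Safety and tolerability are part of the primary objective. Efficacy endpoints, alpha and power are untouched.

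**Working it through.** The plan states no figure for this, so the check is schedule arithmetic.

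**Inputs.** Cycle length is 21 days (6.1; Table 6 footnote e agrees, with 3 cycles = week 9 and 6 cycles = week 18). The panel is due at least every 3 cycles after cycle 6 (footnote c). Treatment lasts up to 24 months (3.4). On vorinostat, the plan says "vorinostat will be given at 400 mg per day (4x 100 mg tablets), 5 of 7 days" (4.1.2).

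**Cycle starts without a required result.** 24 months is about 730 days, and 730 / 21 = 34.8, so there are 34 or 35 cycle starts, of which 28 or 29 follow cycle 6. The first later panel may fall at cycle 7, 8 or 9, then every third cycle.

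| Cycle starts | First panel at cycle | Required panels | Without a result |
|---|---|---|---|
| 34 | 7 | 10 | 18 of 28 (64%) |
| 34 | 8 or 9 | 9 | 19 of 28 (68%) |
| 35 | 7 or 8 | 10 | 19 of 29 (66%) |
| 35 | 9 | 9 | 20 of 29 (69%) |

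**Delay.** The longest wait is 3 x 21 = 63 days against 21 with per-cycle testing, an excess of 63 - 21 = 42 days. With onset uniform over the interval, the mean wait is 63/2 = 31.5 days against 21/2 = 10.5, an excess of 21 days. The excess is 0, 21 or 42 days with probability 1/3 each. At 5 of 7 days, 42 days hold 42 x 5/7 = 30 vorinostat doses. If every cycle slipped by the 5 days that footnote g permits, the maximum excess would be 3 x 26 - 26 = 52 days.

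**Share of all on-treatment cycle starts.** This needs a drop-out assumption. Let s be the fraction still on treatment at 24 weeks (8 cycles). I take s = 0.10 and 0.30 (the null and alternative rates in section 8.2) and 0.40 (the clinical benefit rate in the earlier vorinostat-tamoxifen trial, 1.3.1.1). Using these as on-treatment fractions is my assumption. Only gaps after cycle 6 are counted.

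- Exponential drop-out: cycle c has weight r^(c-1), with r = s^(1/8). The fraction reaching cycle 7 is r^6 = s^0.75.
- Drop-out only at scans: a constant fraction q stays on after each 9-week scan. Two scans fall before 24 weeks, so q = s^(1/2) and the fraction reaching cycle 7 is s. Two of every three later cycle starts lack a result. Ignoring the 24-month cap, the share is [2q²/(1-q)] / [3/(1-q)] = 2s/3. This keeps scans at 3-cycle spacing, although they may be spaced out later.

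| s | Drop-out | Reach cycle 7 | Missing results per patient | Share of all cycle starts |
|---|---|---|---|---|
| 0.10 | exponential | 18% | 0.40-0.54 | 10-13% |
| 0.10 | at scans | 10% | 0.29 | 7% |
| 0.30 | exponential | 41% | 1.75-2.05 | 25-29% |
| 0.30 | at scans | 30% | 1.32 | 20% |
| 0.40 | exponential | 50% | 2.79-3.17 | 31-35% |
| 0.40 | at scans | 40% | 2.14-2.15 | 26-27% |

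Ranges cover the three panel positions and 34 or 35 starts. Overall the share is roughly 7-35%.

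**With the panel every cycle.** The longest required interval falls from 63 to 21 days, and no cycle start lacks a required result.

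**The case against.** The step-down can be defended as deliberate. Testing is dense early (screening, days 1, 8 and 15 of cycle 1, day 1 of cycle 2, then monthly to cycle 6) and relaxes only for patients who have tolerated about 18 weeks. Footnote c is a minimum and allows earlier testing. The vorinostat dose-limiting toxicities listed in 4.1.2 are not hepatic, and 5.1.1.1 describes severe liver abnormalities on tamoxifen as rare and mostly of uncertain relationship. Scans after cycles 6, 9 and 12 also look for progression. All of this stands and limits the weight of the point. It does not reach the silent first rise, because earlier testing needs a clinical prompt.

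The Hepatic Dysfunction sentence could also be read as already expecting a day 1 panel in every cycle. A reader might go further and infer a flat contradiction with Table 6. The text supports neither. The sentence is conditional: it says which value sets the dose once a rise has been found and progression excluded, and it orders no test. What is left is a gap.

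Two sources outside the documents could set more frequent liver testing: the separate guidance on immune-related events (5.1.1.2) and the site guidance for the hepatic criteria in the trial file binder (5.2.2). Neither is available, so this reservation stands.

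Finally, the clause limiting dose changes to clinically relevant, drug-related abnormalities means that some silent rises would change nothing. The 42 days and 30 doses are therefore a worst case.

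**Conclusion.** The point holds as a monitoring gap that is cheap to close. For a patient treated the full 24 months, about two-thirds (64-69%) of cycle starts after cycle 6 carry no required liver result. A first, asymptomatic, clinically relevant, drug-related rise could be found up to 42 days later than with per-cycle testing, or 21 days later on average if onset is uniform. These figures assume nominal 21-day cycles and testing at the required minimum.

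A reader might take two-thirds as the share of the whole trial. It is not: the share of all on-treatment cycle starts is roughly 7-35%, and that range rests on the assumed drop-out pattern and 24-week fractions. Nor do the documents show that patients would be harmed or that the 24-hour report would be missed. They give no rate for late rises, and the reporting rule is not broken if the event is detected later. The separate guidance could narrow or close the gap. No efficacy conclusion depends on it.

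**What to change.** In Table 6, remove footnote c from the comprehensive metabolic panel row and keep it on the tumour-marker row. Require the panel, or at least AST, ALT, bilirubin and alkaline phosphatase, on day 1 of every cycle with the CBC already drawn then.

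The cost is one calendar change in an amendment and one extra chemistry tube at an existing draw. After cycle 6 this means up to 18-20 extra panels for a patient treated the full 24 months. The average is about 0.3-3.2 per patient over the drop-out scenarios: roughly 6-63 panels for 20 patients (0.29 x 20 to 3.17 x 20) and 25-276 for 87 (0.29 x 87 to 3.17 x 87). In cycles 3-6 it adds none if monthly means each cycle, or about one if it means a calendar month. More mild laboratory rises will be found, but the existing clinical-relevance clause limits their effect on dosing. The dose rules, sample size and power do not change.
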